10.1 Demographics

The subject demographic data collected in this study include age, sex, race, ethnicity, and iris color. Subjects who record more than one race will be grouped into a single category denoted as Multi-Racial, and subjects who record more than one iris color will be classified as heterochromia. Sex, race, ethnicity, and iris color will be presented using descriptive summary statistics with frequency counts and percentages. Age (years) will be summarized, overall and by treatment arm, using continuous descriptive statistics. Age will be reported in years and calculated using the following formula:

$$\text{Age} = (\text{Informed Consent Date} - \text{Date of Birth}) / 365.25, \text{ truncated as an integer}$$

Demographic variables will be summarized for the ITT and PP by treatment arm and overall in tables.

A subject listing that includes all demographic variables will also be provided.

10.2 Baseline Characteristics

Baseline characteristics are measured to ensure the safety and eligibility of subjects at Visit 1 (Day -1 to -14) and to confirm their previous results obtained within three months of Visit 1 (Day -1 to -14) have not changed significantly. Subject level listings will be used to present pre-treatment information from the ITT analysis set at the eye level when appropriate. Baseline characteristics will be contained in subject listings only and will include:

- Manifest refraction
- Dark-adapted pupillometry
- Fluorescein staining
- Dilated indirect funduscopy

11. Medical History and Concomitant Medications

11.1 Medical History

Medical history will be coded using Medical Dictionary for Regulatory Activities (MedDRA) Version 21.1. Non-ocular medical history will be summarized using discrete summary statistics and presented by treatment arm at the subject level by System Organ Class (SOC) and Preferred Term (PT) using the Safety analysis set. Ocular medical history will be similarly summarized at the subject level. If a subject reports the same PT multiple times within the same SOC, then that PT will only be reported once within that SOC. As

with the PT, if a subject reports multiple conditions within the same SOC, then that SOC will only be reported once.

Listings of medical history will be generated separately for ocular and non-ocular information.

11.2 Prior and Concomitant Medications

Prior and concomitant medications will be coded using World Health Organization (WHO) Drug Dictionary (WHODrug Global, B3, September 2018) and summarized to the therapeutic drug class (Anatomical Therapeutic Chemical [ATC] 4 classification) and preferred name (generic drug name). If the ATC 4 classification is not provided, the next lowest classification that is provided in the coding dictionary will be employed. The preferred name will be defined as the active ingredient; if the active ingredient is not provided or includes more than two ingredients (eg, multivitamins) then the drug name will be summarized as the preferred name. Any uncoded terms will be summarized under the ATC classification and preferred name of “Uncoded.”

Concomitant medications are defined as those medications listed as having been taken (1) prior to initiation of study drug administration and continuing for any period of time following the first administration of study drug or (2) at any time following the first administration of study drug. Prior medications are defined as those medications not concomitant, but taken within 30 days of screening Visit 1. Prior and concomitant medications will be summarized using the Safely analysis set. Medications will be tabulated for each treatment arm using frequency counts and percentages. Subjects may have more than one medication per ATC text. At each level of subject summarization, a subject will be counted once if reporting one or more medications. Percentages will be based on the number of subjects in each treatment arm.

Summaries will be generated separately for prior and concomitant medications, with ocular and non-ocular data also summarized separately. Subject listings will group prior and concomitant medications together, with ocular and non-ocular information presented separately.

12. Efficacy Analyses

12.2 Secondary Efficacy Analysis

The key secondary efficacy analysis will be the same analysis as the primary analysis, but instead employing the ITT analysis set.

For the assessment of BCVA at 40 cm, the percentage of study eyes achieving a ≥ 3 -line (15-letters) and ≥ 2 -line (10-letters) improvement from baseline for [REDACTED] 1 [REDACTED] hours post-treatment) will be conducted using the PP analysis set.

analyses of these secondary efficacy variables will then be repeated using the ITT analysis set.

11. **What is the primary purpose of the study?** (check all that apply)

The observed BCVA as well as the change from baseline in BCVA will be summarized by treatment group using continuous descriptive summary statistics, and subject-specific BCVA data will also be presented in a listing for each visual range, separately.

A horizontal bar chart consisting of 15 black bars. The first 10 bars are of equal length, while the remaining 5 bars are progressively longer. A vertical dashed line is positioned at the center of the 10th bar. A small black square is located at the bottom left of the chart area.

13. Exploratory Analysis

ther.

14. Safety Analyses

All safety analyses will be conducted using the safety analysis set. BCVA at distance under normal and low luminance testing conditions, findings from slit lamp biomicroscopy examination, conjunctival redness grading and IP drop comfort assessment, as well as IOP measurements will be summarized descriptively.

using quantitative and qualitative summary statistics by treatment arm and subject visit, as appropriate. All such measurements related to safety endpoints will also be presented in a detailed subject listing.

14.1 Adverse Event Summaries

All AEs will be coded using the MedDRA Version 21.1. A Treatment-emergent adverse event (TEAE) is defined as any event that has an onset date on or after the first dose of IP. All AEs collected in the eCRFs will be presented in data listings, but only TEAEs will be summarized in data tables. An overall summary will be presented that includes the number of TEAEs and the number and percentage of subjects who experienced at least one TEAE, by treatment group. This summary will also include breakdowns of TEAEs further categorized as (for ocular and non-ocular separately, where appropriate):

- Ocular TEAEs
- Non-ocular TEAEs
- [REDACTED]
- [REDACTED]
- [REDACTED]
- All SAEs
- [REDACTED]
- [REDACTED]
- TEAEs leading to study discontinuation
- TEAEs by Maximum Severity

Separate summaries (for ocular and non-ocular, where appropriate) will also be provided for these categories of TEAEs by SOC and PT. If a subject reports the same PT multiple times within the same SOC, that PT will only be reported once within that SOC. As with the PT, if a subject reports multiple conditions within the same SOC, that SOC will only be reported once. In the summary, SOC will be listed in ascending alphabetical order; PTs will be listed in order of descending frequency for all subjects within each SOC.

All AEs will be presented in a subject listing, with ocular AEs listed separately from non-ocular AEs. All TEAEs leading to study discontinuation will be listed separately. In addition, all SAEs will be presented in a separate listing.

14.2 [REDACTED]

[REDACTED]
[REDACTED]
[REDACTED]
[REDACTED]
[REDACTED]
[REDACTED]

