9 ADVERSE EVENTS

9.1 Adverse Event

An AE is defined as any untoward medical occurrence associated with the use of an IP in humans, whether or not considered IP-related. An AE can be any unfavorable and unintended sign (e.g. an abnormal laboratory finding), symptom, or disease temporally associated with the use of an IP, without any judgment about causality. An AE can arise from any use of the IP (e.g. off-label use, use in combination with another drug or medical device) and from any route of administration, formulation, or dose, including an overdose.

All AEs spontaneously reported by the subject and/or in response to an open question from study personnel or revealed by observation, physical examination, or other diagnostic procedures will be recorded in the subject's source document and eCRF. Any clinically relevant deterioration in clinical finding is considered an AE and must be recorded. When possible, signs and symptoms indicating a common underlying pathology should be noted as one comprehensive event.

Documentation regarding the AE should be made as to the nature, date of onset, end date, severity, relationship to IP, expectedness, action(s) taken, seriousness, and outcome of any sign or symptom observed by the physician or reported by the patient upon indirect questioning.

All AEs will be collected from the time a subject signs the ICF through the subject's study exit visit.

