10.10 Safety Analysis

Verbatim descriptions of AEs will be mapped to Medical Dictionary for Regulatory Activities (MedDRA) terms and be presented in a data listing. Treatment emergent AEs (TEAEs), those that occur after the first dose of IP within each period, will be summarized by treatment group using frequency and percent for each system organ class (SOC) and preferred term (PT) within each SOC. Similar summaries will also be presented for TEAEs related to the IP and by severity. When reporting the incidence of AEs, a subject will only be counted once if they ever experience an event within the SOC and ever experience the individual PT within the specific treatment period. AEs will be reported separately by period.

[REDACTED]

Full details of the safety analyses will be specified in the formal SAP.

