3.2 Schedule of Visits and Measurements

The schedule of visits and assessments is provided in Table 2.

[figure not shown]

Figure 1. Study Design and Study Visitation

[figure not shown]

Table 2. Schedule of Visits and Assessments

A large black rectangular redaction box covering the majority of the page content, from just below the caption to just above the page footer.

4. Study Treatments

The IP is CSF-1, a topical eye drop solution for [REDACTED] presbyopia, which works by reducing the natural pupil size and correspondingly increasing the depth of field. The formulation developed by Orasis Pharmaceuticals Ltd. is a viscous eye drop containing the active ingredients pilocarpine hydrochloride and diclofenac sodium with the addition of excipients, [REDACTED]

[REDACTED]. The inclusion of a non-steroidal anti-inflammatory drug (diclofenac sodium) may reduce the inflammatory response induced by pilocarpine hydrochloride. Pre-treatment ophthalmic assessments will be repeated at Day 1. Following the pre-treatment assessments, qualified subjects will be randomized to 1:1:1 to one of the following treatment arms:

- CSF-1: pilocarpine hydrochloride (0.2% [low dose])/(0.4% [high dose]) and diclofenac sodium (0.006%)
- Pilocarpine hydrochloride (0.2% [low dose])/(0.4% [high dose])
- Diclofenac sodium (0.006%)

After randomization, subjects will receive IP and a dosing diary. Once dispensed to the subject, IP [REDACTED] Subjects will be instructed to save and return all used and unused IP and to bring their kits to each study visit. Subjects will be instructed to dose bilaterally BID in the morning and afternoon ([REDACTED] and record doses in their diary (paper). Subjects should not dose before the morning of Day 8. At Day 8, subjects will receive their morning dose from study site personnel, after the required pre-treatment assessments, and the current IP will be collected.

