Subjects will be assigned a new IP at the conclusion of Day 8 and instructed on the use of a new dosing diary. The afternoon dose, from the new IP, will be instilled in-office during Day 8. After subjects receive their IP and dosing diary, subjects will be instructed to dose bilaterally BID in the morning and afternoon ([REDACTED]) and record doses in their diary until Day 15. Subjects should not dose before the morning of Day 15. At Day 15, subjects will receive their last dose from study site personnel, after the required pre-treatment assessments, and the current IP will be collected. Subjects will exit the study after all assessments are complete at Day 15.

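### Adverse events starting on Day 8 cannot be tied to 0.2% or 0.4% pilocarpine from the onset date alone, and the TEAE definition makes no provision for worsening

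*SAP*

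**What the plan says.** **Dosing on Day 8.** SAP Section 4 (Study Treatments) states: "At Day 8, subjects will receive their morning dose from study site personnel, after the required pre-treatment assessments". The first kit is then collected. The same section continues: "The afternoon dose, from the new IP, will be instilled in-office during Day 8". SAP Section 3.1 makes this the step from 0.2% to 0.4% in the CSF-1 and pilocarpine-alone arms. The diclofenac arm stays on the same product.

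**Protocol rule.** Protocol Section 10.10 defines treatment-emergent events as "those that occur after the first dose of IP within each period". It counts each preferred term (PT) within the treatment period and adds: "AEs will be reported separately by period".

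**SAP rule.** SAP Section 14.1 gives a single definition with no reference to period: "A Treatment-emergent adverse event (TEAE) is defined as any event that has an onset date on or after the first dose of IP". It adds that "only TEAEs will be summarized in data tables", with the remaining events going to listings. Its counting rule is: "If a subject reports the same PT multiple times within the same SOC, that PT will only be reported once within that SOC".

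**What is recorded.** Protocol Section 9.1 states: "Documentation regarding the AE should be made as to the nature, date of onset, end date, severity". The list continues with relationship, outcome and similar items, but no onset time. Collection starts at consent, before any IP. The same section treats a clinically relevant deterioration in a clinical finding as an AE.

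**Precedence.** SAP Section 1 says its methods supersede the protocol's. SAP Section 16 declares no change from the protocol.

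**The concern.** Safety and tolerability at two pilocarpine concentrations is a stated secondary objective, and Protocol Section 10.10 serves it by reporting events per period. That works only if each event can be placed in a period. Day 8 belongs to both periods, and the recorded item is a date.

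Day 8 may also carry more than its share of low-dose findings. In the readable text, Visits 3 and 4 are the only visits with in-clinic safety assessments after an IP dose (end-of-visit slit lamp, post-treatment redness), and Protocol 9.1 counts findings from observation or examination as AEs. A finding first seen after the morning 0.2% dose has the same date as the first 0.4% dose.

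The second gap concerns severity. A dose step-up is where existing symptoms might be expected to get worse, and neither definition says how a worsened event is classified or which concentration it counts under.

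**Working it through.** The plan contains no adverse event rate, so there is no figure of its own to reproduce. The check sets the rules against the dosing timetable and then adds an illustration on assumed rates.

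**Step 1: can a Day 8 onset be placed?** Take an event in a pilocarpine arm that starts between the two Day 8 doses.
- Protocol 10.10, read literally: it has not occurred after the first dose of period 2, so it belongs to period 1.
- The SAP's on-or-after date wording, if it were carried over to period 2: the onset date equals the date of the first 0.4% dose, so it belongs to period 2.
- An event starting after the afternoon dose has an identical date record.

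The literal protocol rule separates the two events but needs the order of onset and dose. The listed data item does not supply it. On Day 1 the same date comparison makes an onset before the first dose treatment-emergent.

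**Step 2: where does a worsening event go?** Assume no new record is opened.

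| Event | SAP 14.1 status | Consequence |
|---|---|---|
| Starts after consent on a date before the first IP dose, worsens on IP | Not a TEAE | Listed, not tabulated |
| Starts on 0.2%, worsens on 0.4% | TEAE, one onset date | Tabulated, with no stated place in the 0.4% results |

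If a second record is opened in the second row, the SAP still counts the PT once per subject with no period qualifier, so the readable rule does not say that it adds to a 0.4% count.

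**Step 3: size, on assumptions.**
- Low-concentration doses per eye: Days 1 to 7 twice daily, 7 × 2 = 14, plus Day 8 morning = 15 (14 if only one dose is taken on Day 1).
- High-concentration doses per eye: Day 8 afternoon 1, Days 9 to 14 6 × 2 = 12, Day 15 morning 1, total 14.
- The Day 8 morning dose is 1/15 of low-concentration dosing.

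Let r be the true incidence at each concentration (assumed equal) and f the share of low-dose events that start on Day 8. Suppose every such event is booked to the high dose, in subjects not already counted there:

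low shown = r(1 − f); high shown = r(1 + f)

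| r (assumed) | f = 1/15 | f = 1/4 | f = 1/2 |
|---|---|---|---|
| 10% | 9.3% v 10.7% | 7.5% v 12.5% | 5% v 15% |
| 20% | 18.7% v 21.3% | 15% v 25% | 10% v 30% |
| 30% | 28% v 32% | 22.5% v 37.5% | 15% v 45% |

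For example, with r = 20% and f = 1/15: 20 × 14/15 = 18.7 and 20 × 16/15 = 21.3. With 50 per arm, r = 20% and f = 1/4, that is 7.5 against 12.5 subjects instead of 10 and 10. A convention that booked all Day 8 onsets to the low dose would err the other way.

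**The case against.** **No period rule by date exists.** A reader might infer that the SAP assigns events to a concentration by onset date and so moves 0.2% events into the 0.4% column. The documents do not support that. The SAP sentence only separates treatment-emergent from other events, and Protocol 10.10 speaks of events occurring after the first dose in the period, which, taken literally, places a pre-afternoon event correctly. This stands: misassignment is possible, not stated. What remains is that the listed data cannot carry out the protocol rule on Day 8.

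**Missing text may answer it.** The eCRF is not in the documents, the list in Protocol 9.1 does not claim to be complete, and parts of SAP 14.1, all of 14.2, the table list and most visit procedures are redacted or missing. An onset-time field or period rule may be there. This stands, and the fix is conditional on it.

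**Worsening is partly covered.** A reader might infer that worsening events drop out altogether. They need not. Protocol 9.1 lets a deteriorating clinical finding be recorded as an AE, an event that starts on 0.2% is a TEAE in any case, and SAP 14.1 also tabulates maximum severity. But 9.1 does not say that worsening of an already recorded event or symptom gets its own record and date, and maximum severity is not tied to a concentration in the readable text.

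**Other safety data are visit-specific.** Redness and slit lamp are assessed after dosing at Visits 3 and 4, and safety measures are summarised by arm and visit as appropriate. True, so tolerability by concentration does not rest on AE tables alone.

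**Conclusion.** The point holds in limited form. Protocol 10.10 requires reporting by period. For Day 8 onsets in the two pilocarpine arms, the readable data items cannot deliver it, and the readable SAP drops the period from both definition and counting while Section 16 declares no change. Separately, the onset-only definition leaves a pre-dose event that worsens on IP out of the tables unless it is re-recorded, and gives an event that worsens after the step-up no stated place in the 0.4% results.

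The size is unknown. At an assumed 20% incidence it runs from 18.7% v 21.3%, if onsets follow dose share, to 15% v 25% if a quarter of low-dose events start on Day 8. Both figures assume that every such event is booked to the high dose, in subjects not already counted there. A reader might infer a much larger distortion: 6 of 10 low-dose events moving in an arm of 50 would show 4/50 = 8% against 16/50 = 32%. That needs a 60% Day 8 share, which nothing in the documents supports. Sample size, power and alpha are unaffected.

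**What to change.** 1. Unless the eCRF already has it, record onset time, or a box for before or after the first dose from this kit, for AEs with onset on Day 1 or Day 8. Assign Day 8 events by whether they began before or after the first dose from the Visit 3 kit, and state a rule for unknown timing.
2. In Protocol 10.10 and SAP 14.1, define a TEAE as an event that starts, or worsens in severity, after the first dose of IP in that period. Tell sites to record worsening under its own date.
3. In SAP 14.1, count PTs within period and report by period, as Protocol 10.10 does. Otherwise declare the departure in SAP Section 16.

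If redacted text already contains a time field or period rule, pointing to it settles item 1; the worsening clause would still need an answer. The cost is one eCRF item, a completion guideline and a few sentences in each document. TEAE counts would be slightly higher. Timing should be captured when the event is reported, because it is hard to recover later.

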14.3 Slit-Lamp Biomicroscopy Examination

A slit lamp biomicroscopy examination of the eyelid, conjunctiva, cornea, anterior chamber, iris, and lens will be conducted on both eyes at all scheduled visits pre-treatment, and an end of visit slit lamp will also be completed at Visits 1, 3, and 4. Magnification will be consistent with the investigator's standard clinical practice. The subject will be seated for the examination. The results will be graded as normal, abnormal not clinically significant (NCS), or abnormal clinically significant (CS). A table will summarize the findings utilizing frequency counts and percentages for each treatment group at each time point and for each eye (study eye and fellow eye). Percentages will be based on the number of subjects in each treatment group with responses. A subject listing of the slit-lamp parameters will also be produced.

14.4 Conjunctival Redness Assessment

A conjunctival redness assessment is conducted at pre-treatment for all visits and at post-treatment for Visits 3 and 4 utilizing the █ Redness Scale #6.0 Conjunctival Redness Assessments. The investigator will evaluate ocular redness of the three vessel beds (under the slit lamp) and grade according to the following scale:

14.5 IP Drop Comfort Assessment

14.6 Intraocular Pressure

Intraocular pressure will be assessed via Goldmann applanation tonometry at Visits 1, 3, and 4. Results will be taken from a single measurement and will be recorded in mmHg. The IOP values and changes from baseline for each eye (study eye and fellow eye) will be summarized using continuous descriptive statistics by visit and eye for each treatment group. A subject listing of IOP results will also be produced.

15. Interim Analyses

An interim analysis has not been planned or performed for this study.

16. Changes from Protocol-Stated Analyses

As of the date of this SAP, the protocol-stated analyses have not been changed.

17. References

US Federal Register. (1998) International Conference on Harmonization; Guidance for Industry: Statistical Principles for Clinical Trials. Department of Health and Human Services: Food and Drug Administration. Federal Register, Vol. 63, No. 179, September 16, 1998, page 49583. (E9)

US Federal Register. (1996) International Conference on Harmonization; Guidance for Industry: Structure and Content of Clinical Study Reports. Department of Health and Human Services: Food and Drug Administration. Federal Register Vol. 61, July 17, 1996, page 37320. (E3)

[figure not shown]
Kenward MG and Roger JH (1997), "Small Sample Inference for Fixed Effects from Restricted Maximum Likelihood," *Biometrics*, 53, 983–997. DOI: 10.2307/2533558

18. Revision History

Documentation of revision to the SAP will commence after the approval of Version 0.1.

19. Tables

Tables that will be included in the topline delivery are shown in boldface italics.

21. Figures

Figures may be produced at the discretion of the study sponsor.
